7.5 Secondary Endpoints - Biomarker

7.5.1 Definition

The following biomarkers will be used in the analyses.

ANC/ALC (Absolute neutrophils count / Absolute Lymphocytes count)

C-Reactive Protein (CRP)

D-Dimer

Procalcitonin

Il-6

Il-8

Absolute and percent change will be calculated for each biomarker.

7.5.2 Analysis

No statistical tests will be performed.

7.5.3 Presentation

All biomarkers will be presented using summary statistics and graphs showing both the mean, absolute and percent change over time.

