## **10.4 Statistical Analyses Plan**

A Statistical Analysis Plan (SAP) detailing the analyses for the study will be developed prior to the database lock. The SAP will serve as the final arbiter of all statistical analyses. Data will be summarized using descriptive statistics only. Continuous data will be summarized with number of patients (n), mean, median, minimum, maximum, standard of deviation, coefficient of variation and or geometric mean. Categorical data will be summarized with number and proportion of patients. The number of patients randomized in the study and the number of patients completing assessments for each Day will be summarized by cohort, sex and treatment arm. The number of patients and reasons for discontinuation of CM4620-IE or withdrawal from the study will be summarized.

Efficacy endpoints that will be analyzed will include, but not limited to, SIRS score, APACHE II score, CT severity index scores, classification indexes, organ failure scores, SOFA score, biomarker values and pain scores. These endpoints will be further detailed in the SAP.

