4.5 Summary Statistics

In general, all data collected will be presented with summary statistics and given in patient data listings. Summary statistics will include at least number of patients, mean, standard deviation, median, minimum and maximum for continuous data and frequency and percentage for categorical data. Table with summary statistics will be divided by treatment group and dose group, and visit where applicable. Patient data listings will be sorted by treatment, subject and timing of assessments.

For confidence intervals for proportions will the Clopper-Pearson exact formula be used.

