4.8 Handling of Drop-outs, Missing Data and Outliers

Outliers will be included in summary tables and listings, and will not be handled separately in any analyses. No imputation of missing data will be performed (however, will data entered in unscheduled visit be placed to the nearest applicable visit with missing values).

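### The biomarker percent-change graph, read as an arithmetic mean, is biased upward relative to the typical patient, by an amount that depends on a spread the documents do not give

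*SAP*

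**What the plan says.** SAP 7.5.1 lists six markers (ANC/ALC, CRP, D-dimer, procalcitonin, IL-6, IL-8) and derives only raw changes: "Absolute and percent change will be calculated for each biomarker". No log transformation is mentioned. SAP 7.5.2 adds "No statistical tests will be performed". SAP 7.5.3 then sets the display: "All biomarkers will be presented using summary statistics and graphs showing both the mean, absolute and percent change over time". It names no measure of spread for these graphs, whereas SAP 7.3.3 specifies means with two standard errors for the PASS graphs.

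The tables follow SAP 4.5: "Summary statistics will include at least number of patients, mean, standard deviation, median, minimum and maximum for continuous data". The same section provides patient data listings. On extreme values, SAP 4.8 says: "Outliers will be included in summary tables and listings, and will not be handled separately in any analyses". It also rules out imputation of missing data.

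Protocol 10.4 includes in its list of summaries "standard of deviation, coefficient of variation and or geometric mean" and gives the SAP precedence: "The SAP will serve as the final arbiter of all statistical analyses". SAP 4.5 names neither the coefficient of variation nor the geometric mean, and SAP 8, which is meant to hold changes from the protocol, has no entry. Neither document states a standard deviation, a distribution or an expected change for any biomarker.

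**The concern.** Percent change is asymmetric: a doubling counts as +100% and a halving as only -50%. Averaged arithmetically over patients, it gives rises more weight than equivalent falls. Inflammatory markers are positive and probably right-skewed. Protocol 1.1 describes a disease that is mostly mild and self-limiting, with 15–20% of patients developing the severe form, so a few very high values are plausible even though entry is enriched for SIRS or hypoxemia.

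As biomarkers are not tested, the tables and graphs are the whole biomarker result. The groups are small, and SAP 4.11 splits every secondary endpoint by gender as well. A reader of the percent-change graph could see a rise where the typical patient has none, or miss a fall where the typical patient has one.

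**Working it through.** **Group sizes.** Protocol 3.1 gives cohorts of 4, 4, 8 and 8, and 4 + 4 + 8 + 8 = 24, which reproduces the stated total. At 3:1, a cohort of 4 gives 3 active and 1 control, and a cohort of 8 gives 6 active and 2 control. The displayed groups are therefore 6 controls, 6 at the first-phase dose and 12 at the second-phase dose. By sex there are 1 + 2 = 3 controls.

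**Direction, with no assumption about spread.** For positive ratios to baseline, the arithmetic mean is never below the geometric mean.
- Half the patients double and half halve: mean percent change = (100 - 50)/2 = +25%; geometric mean ratio = (2 × 0.5)^(1/2) = 1, a change of 0%.
- Five of six controls unchanged, one up tenfold: mean = 900/6 = +150%; geometric mean = 10^(1/6) = 1.47, or +47%; median 0%.
- Two of three controls of one sex unchanged, one up tenfold: mean = 900/3 = +300%; median 0%.

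**Size, with assumed spread.** Assume the ratio to baseline is log-normal with median 1 and log-SD s. Then expected mean percent change = 100 × (exp(s²/2) - 1), while the median and geometric mean change are 0. If the typical patient truly falls by 30%, it is 100 × (0.7 × exp(s²/2) - 1). The last two columns come from 200,000 simulated groups with no typical change.

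| s (assumed) | s²/2 | Expected, typical change 0% | Expected, typical change -30% | Chance plotted mean exceeds +50%, n = 6 | Same, n = 12 |
|---|---|---|---|---|---|
| 0.3 | 0.045 | +5% | -27% | <1% | <1% |
| 0.5 | 0.125 | +13% | -21% | 8% | 3% |
| 0.8 | 0.32 | +38% | -4% | 33% | 32% |
| 1.0 | 0.50 | +65% | +15% | 47% | 53% |
| 1.5 | 1.125 | +208% | +116% | 68% | 81% |

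Solving s = sqrt(2 × ln(1 + k)), the expected artefact reaches +20% at s = 0.60, +50% at 0.90 and +100% at 1.18.

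These are expectations. The plotted mean is itself skewed, so a single small group will often show less. At s = 1.5 the median plotted value is +114% for n = 6 and +144% for n = 12. The sample median under the same conditions is +8% and +2%.

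**The other two graphs.** If a marker has the same distribution at baseline and follow-up, the expected mean is flat and the expected absolute change is 0. Percent change still rises. With log-SD 1.0 at both times and correlation 0.5, s² = 2 × 1.0² × (1 - 0.5) = 1.0, giving +65%.

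**Between groups.** With the same median ratio and s in every group, the expected inflation is the same in every group, so there is no expected difference between them. Chance differences are larger, though. The simulated chance that groups of 6 and 12 differ by more than 50 percentage points, with no true difference, is as follows.

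| s (assumed) | Mean percent change | Geometric mean ratio |
|---|---|---|
| 0.5 | 9% | 5% |
| 0.8 | 39% | 22% |
| 1.0 | 56% | 32% |
| 1.5 | 81% | 49% |

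**The case against.** The strongest reply is that little depends on these graphs. Biomarkers are secondary, descriptive and untested, in a study that Protocol 10.1 says is not powered for inference. The SAP 4.5 tables and listings already show the typical and the extreme patient, which are easy to find in groups of 6, 6 and 12. All of that stands, and it limits the point to the graphs.

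Four stronger readings are tempting, and the documents do not support them.
- A reader might infer that the graphs will show large rises. That needs a log-SD, and none is given. At 0.3 to 0.5 the artefact is only +5% to +13%.
- A reader might blame all three graphs. The systematic bias belongs to percent change only. Moreover, SAP 7.5.3 does not name the statistic plotted for change, so the arithmetic mean is the natural reading, not a stated fact.
- A reader might say that the SAP removes a summary the protocol requires. The protocol makes the geometric mean optional ("standard of deviation, coefficient of variation and or geometric mean"), SAP 4.5 sets a minimum list and not a closed one, and the SAP governs. At most, an optional statistic is not carried forward and SAP 8 does not comment on it.
- A reader might infer that the method biases the comparison with control. With equal spread in each group it does not in expectation. What remains is extra sampling noise, which a geometric mean reduces but does not remove.

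Keeping outliers is not an error either. The remedy below keeps them too.

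**Conclusion.** The point holds for the percent-change graph. Arithmetic mean percent change equals or exceeds the geometric mean change in any data set of positive ratios, and the SAP plans no log-scale, geometric or median graph beside it. The direction is certain once the plotted statistic is an arithmetic mean.

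The size is conditional on a log-normal ratio with median 1 and on assumed log-SDs, over which the expected artefact runs from negligible to more than a doubling. At a log-SD of about 1.0 or more, a true 30% fall in the typical patient would be expected to plot as a rise. At 0.5 or less, the picture would be only modestly distorted.

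The mean and absolute-change graphs are open to domination by one extreme patient, but not to this systematic upward shift. No test, decision rule or primary safety result changes. This is a presentation weakness worth correcting before database lock.

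**What to change.** In SAP 7.5.3, replace the arithmetic mean percent-change graph with the geometric mean ratio to baseline, or the median ratio, by group and visit on a log scale, with individual patient lines behind it. Groups of 6, 6 and 12 are small enough for every patient to be shown. Add the log ratio to baseline to the derived variables in SAP 7.5.1, and the geometric mean and geometric CV to the biomarker tables. The median, minimum and maximum stay. A 95% confidence interval on the log scale is optional and should be labelled descriptive.

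The cost is SAP wording and some reprogramming; no new data are needed. The downside is that logs cannot take zero, and values below quantification have no exact ratio, while SAP 4.8 bars imputation of missing data. The SAP must therefore state a rule, for example plotting the median ratio for any marker and visit where such values occur. A rule for baseline values of this kind is needed in any case, because percent change also divides by baseline.

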7.6 Secondary Endpoints - SIRS

7.6.1 Definition

SIRS consist of 4 components; temperature of $< 36^{\circ}\text{C}$ or $> 38^{\circ}\text{C}$, heart rate > 90 beats per minute, respiratory rate >20 breaths per minute or $\text{PaCO}_2 < 32$ mmHg and white blood cells (WBC) $> 12,000$ mm^3 , <4000 mm^3 or $> 10\%$ immature band forms. SIRS is present if two or more of the 4 components are identified. If any of the 4 components are missing, that component will not contribute to the SIRS evaluation.

The total SIRS score is the sum of all SIRS components at each time point

Time to resolution of SIRS will be defined as time from randomization to first sign of resolution of SIRS.

The number of days alive and free from SIRS

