### 8.2 Day 1 (0 hour to < 24 hours)

Perform the following procedures immediately prior to randomization of female patients into Cohort 1 (Cohort 3 during the second phase), and the randomization of male patients into Cohort 2 (Cohort 4 during the second phase):

- Record vital signs

- Record concomitant medications
- Draw a blood sample for CBC, differential and platelets, Chemistry Profile, serum biomarkers—send to central lab
- Obtain a urine sample for biomarker testing—send to central lab
- Record SpO2 and the FiO2 and time performed
- If an ABG has already been performed as part of standard of care, record the pH, PaCO2, PaO2, SaO2 and the FiO2 at the time of draw
- Calculate the Glasgow Coma Scale score
- Record patient's pain using the PNRS
- Assess pain using the CPOT
- **Randomize patient**

If the patient has been randomized to receive CM4620-IE:

- **Start the administration of CM4620-IE (1st dose) as soon as possible after randomization and preferably within 6 hours (up to 8) from the time the patient or legal representative signed the informed consent;**
- If the administration of CM4620-IE is started more than 8 hours from the time the patient or legal representative provided informed consent, note the time and inform the Medical Monitor;
- Draw a blood sample for PK 30 minutes ( $\pm 15$  minutes) after completing the administration of CM4620-IE—send to central lab
- Draw a blood sample for PK 8 hours ( $\pm 30$  minutes) after completing the administration of CM4620-IE—send to central lab

For all patients, at 12 hours ( $\pm 1$  hour) from time of randomization:

- Record vital signs
- Draw a blood sample for CBC, differential and platelets—send to central lab
- Perform an AE/SAE assessment

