### 8.11.5 Vital Signs

The recorded vital signs must include the patient’s current temperature, heart rate (beats per minute), systolic and diastolic blood pressures, respiratory rate (breaths per minute), and the total input and output of fluids. The highest and lowest temperatures, the highest heart rate, and the highest respiratory rate since the prior study-required assessment will also be recorded. The total input of fluids (oral and intravenous) and the total output of fluids (urine output and nasogastric output) since the prior study-required assessment will be recorded.

If the patient has been started on vasopressor therapy since the prior study-required assessment, the start time should be recorded. If the patient has been placed on renal replacement therapy since the prior study-required assessment, the type of therapy will be recorded. If the patient has been placed on mechanical ventilation since the prior study-required assessment, the type of ventilation will be recorded (noninvasive or invasive mechanical ventilation). The current settings for fraction of inspired oxygen (FiO2), respiratory rate, tidal volume and positive end-expiratory pressure (PEEP) at the assessment will be recorded. If intra-abdominal pressures are being monitored, the current pressure and the highest pressure since the prior study-required assessment should be recorded. All solid food intake since the prior study-required assessment will be recorded including the time and date of the meal, the percent of the meal completed, if there were nausea or vomiting with the meal, and if pain medications had to be given one hour prior to or after the meal to treat symptoms due to ingesting the meal.

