### **8.11.9 Laboratory Analyses**

At Screening, an amylase or lipase, CBC, differential, and platelets, will be performed at the local lab. The results of the CBC will be used to determine the presence of SIRS. On Days 1 – 5, a CBC, differential, and platelet count will be drawn twice, and chemistry profile will be drawn once, and sent to the central lab. On Days 6 – 10, a CBC, differential, platelet count, and chemistry profile will be collected once and sent to the central lab. The chemistry profile sent to the central lab will consist of sodium, potassium, chloride, bicarbonate, blood urea nitrogen, creatinine, glucose, calcium, total protein, globulin, albumin, alkaline phosphatase, alanine transaminase (ALT), aspartate transaminase (AST), total bilirubin, lactate dehydrogenase (LDH), total cholesterol and triglycerides. The results from these laboratory samples will not be available to the PI or treating physician for the management of the patient with acute pancreatitis.

The PI or treating physician will order all laboratory testing necessary for the management of the patient and analysis will be performed at the local laboratory. Other than at Screening, and all venous and arterial blood gas testing, the blood samples for laboratories ordered as part of the protocol, will be tested at a central lab, and will not be available to assist the PI or treating physician in managing the patient.

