3.1.4 Secondary endpoints

The secondary efficacy endpoints are:

- CTSI Score categorized into Mild, Moderate and Severe
- Balthazar score
- Pancreatic Parenchymal Necrosis
 - < 30%
 - 30-50%
 - > 50%
- PASS score
- Tolerating Solid Food
 - Time to tolerating solid food
 - Arithmetic mean of time to tolerate 50% solid food
- Biomarker measurements including, but not limited to:
 - ANC/ALC (Absolute neutrophils count / Absolute Lymphocytes count)
 - C-Reactive Protein (CRP)
 - D-Dimer

- Procalcitonin
- IL-6
- IL-8
- SIRS
 - Time to resolution of SIRS
 - The number of days alive and free from SIRS
 - Total SIRS score
- Any Organ Failure (LISTINGS)
- Respiratory Failure (LISTINGS)
- Renal Failure (LISTINGS)
- Cardiovascular Failure (LISTINGS)
- Sequential Organ Failure Assessment (SOFA):
 - Respiration Score
 - Coagulation Score
 - Liver Score
 - Cardiovascular Score
 - Central Nervous System Score
 - Renal Score
 - SOFA total Score
- Modified Sequential Organ Failure Assessment (MSOFA):
 - Modified total SOFA Score
- Severity as defined by Revised Atlantic Classification of Acute Pancreatitis
- Severity as defined by Determinant Based Classification of Acute Pancreatitis
- APACHE II score
- Pain Numeric Rating Scale (PNRS) score
- Critical-Care Pain Observation Tool (CPOT) score
- Overall Survival (Listings)
- Number of hospitalized days
 - Total Days
 - Days in Intensive Care

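### SAP 7.6.1 treats a missing SIRS component as not met, so a missed white cell count can fix a false resolution time in a patient with exactly two criteria met, one of them WBC

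*SAP*

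**What the plan says.** SAP 7.6.1 calls SIRS present when at least two of four components (temperature, heart rate, respiration, white cells) are met. On incomplete data it says: "If any of the 4 components are missing, that component will not contribute to the SIRS evaluation". It adds: "Time to resolution of SIRS will be defined as time from randomization to first sign of resolution of SIRS". It gives no not-evaluable status and does not lower the threshold when fewer components are observed. No confirmation at a later time point is required.

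SAP 3.1.4 lists three SIRS outputs among the secondary endpoints: time to resolution, total score, and "The number of days alive and free from SIRS". SAP 7.6.1 repeats the last of these without defining a SIRS-free day.

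On missing data in general, SAP 4.8 says: "No imputation of missing data will be performed". Its one relief is to move values from unscheduled visits to the nearest visit that lacks them. SAP 7.3.1, however, tells the analyst to use the last earlier blood count for the SIRS part of PASS when a 12-hour window contains no WBC.

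On data collection, protocol 8.11.5 says of vital signs: "The highest and lowest temperatures, the highest heart rate, and the highest respiratory rate since the prior study-required assessment will also be recorded". For Days 1 to 5, protocol 8.11.9 says that "a CBC, differential, and platelet count will be drawn twice" each day; from Day 6 it is drawn once a day. Protocol Appendix 11 places both vital signs and blood counts every 12 hours on Days 1 to 5.

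On reporting, SAP 7.6.2 plans no tests and 7.6.3 names only the total score for presentation. Resolution time is summarised only through the general text in SAP 4.5 and the opening of SAP 7. SAP 4.5 says: "Table with summary statistics will be divided by treatment group and dose group, and visit where applicable".

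**The concern.** With the threshold held at two, a component that adds nothing to the count has the same effect as one observed to be normal. A patient with a raised heart rate and a raised WBC has SIRS. If that blood count is missed, the same patient scores one and is classed as free of SIRS. The first-sign rule takes that moment as the resolution time, and a complete assessment 12 hours later that again shows SIRS does not reset it.

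WBC is the most plausible component to be missing. The other three come from bedside recordings, which also capture extremes since the previous assessment, whereas WBC needs a separate central-laboratory sample.

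The plan also contradicts itself. At one time point a patient could meet the WBC criterion within PASS, by use of the earlier count, and be recorded as SIRS-resolved under 7.6.1. In the summary tables a gap in the data could not be told apart from recovery, although listings would show the missing value.

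**Working it through.** The plan states no figure for this point, so there is nothing to reproduce. The check has four steps.

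**1. Which patterns flip.** Four components, each met or not met, give 16 patterns. SIRS is present in 6 + 4 + 1 = 11 of them (exactly two, three or four met).
- Any one component missing, exactly two met: 6 patterns × 4 possible missing components = 24 cases. Status flips when the missing component is one of the two met: 6 × 2 = 12 of 24.
- Three or four met: at least two remain after losing one, so nothing flips. With none or one met, SIRS is truly absent.
- Only WBC missing: 3 of the 6 two-criterion patterns flip (WBC plus one of temperature, heart rate or respiration), which is 3 of the 11 SIRS-present patterns.

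**2. One patient path (assumed).** Heart rate criterion met from 0 to 72 h, WBC criterion met from 0 to 60 h, WBC missed at 12 h only. True resolution is at 72 h.
- SAP 7.6.1: 12 h.
- Latest earlier WBC, as in 7.3.1: 72 h. A value to carry exists, because a blood count is among the Day 1 procedures in protocol 8.2: "Perform the following procedures immediately prior to randomization of female patients into Cohort 1".
- Not evaluable when the missing component could decide status: 72 h.

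The error is 72 − 12 = 60 h. Randomization at 3:1 in cohorts of 4, 4, 8 and 8 gives 1 + 1 + 2 + 2 = 6 patients on supportive care alone, 3 + 3 = 6 on the first-phase regimen and 6 + 6 = 12 on the second-phase regimen. This one error moves a group mean by 60/6 = 10 h or 60/12 = 5 h.

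**3. How often.** The documents give no missing rate, so p = 2%, 5% and 10% are assumptions. It is also assumed that SIRS is evaluated every 12 hours, that only WBC can be missing, and that the patient is the worst case: exactly two persistent criteria, one being WBC. Post-randomization blood counts at 12, 24, …, 108 h number 9, of which 4 fall by 48 h.
- Independent misses: P = 1 − (1 − p)^n.
- Misses clustered within patient (beta-binomial, intraclass correlation ρ = 0.3, assumed): P = 1 − Π (β + i)/(α + β + i) for i = 0 to n − 1, with α = p(1 − ρ)/ρ and β = (1 − p)(1 − ρ)/ρ.

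| Probability of a false resolution | p = 2% | p = 5% | p = 10% |
|---|---|---|---|
| 9 counts, independent | 0.166 | 0.370 | 0.613 |
| 9 counts, clustered | 0.080 | 0.189 | 0.346 |
| 4 counts, independent | 0.078 | 0.185 | 0.344 |
| 4 counts, clustered | 0.052 | 0.127 | 0.243 |

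If 10% to 30% of the 24 patients fit the pattern (assumed) and p = 5%, the expected number with a false time runs from 24 × 0.10 × 0.127 = 0.30 (4 counts, clustered) to 24 × 0.30 × 0.370 = 2.66 (9 counts, independent). The two ends differ in horizon and in clustering as well as in the share of patients.

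**4. Total score.** A missed WBC lowers the score by one point if the WBC criterion was met. With p = 5% and the criterion met at 60% of assessments (assumed), the mean falls by 0.05 × 0.6 = 0.03 points.

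**The case against.** The strongest reply concerns consequence. These are secondary endpoints in an unpowered, descriptive study; no tests are planned; and the only SIRS output that SAP 7.6.3 names is the total score, which moves by about 0.03 points. All of this stands. Resolution time is still a listed endpoint that the general text sends to the tables, and those tables also give the median, which one false value may barely move.

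The 12-hour grid is not fixed by the SAP, which speaks only of time points. SAP 7 presents results by visit, and protocol 3.1 describes daily assessments. If status is derived once per day, the second blood count on Days 1 to 5 can fill the gap and the probabilities fall. This stands too. So does the point that WBC as the likely gap is an inference, since vital signs and blood counts are scheduled together.

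SAP 4.8 is no answer, because moving unscheduled values helps only where such a value exists.

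A reader might draw three stronger conclusions that the documents do not support:
- That any missed WBC produces a false resolution. It does so only when exactly two criteria are met and WBC is one of them.
- That SIRS-free days are necessarily inflated. The SAP does not define such a day, and a second assessment on the same day could still show SIRS.
- That the rule favours CM4620-IE. Nothing shows that blood counts would be missed more often in one arm.

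How resolution time should apply to patients admitted on oxygenation alone is a separate question.

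**Conclusion.** The concern holds in a limited form. That SAP 7.6.1 equates a missing component with one not met, and that the first-sign rule makes the resulting error permanent, follows from the text and needs no assumption. So does the inconsistency with SAP 7.3.1. SIRS-free days may also be overstated, depending on a derivation that the SAP leaves open.

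The size rests on assumptions. For the worst-case patient on a 12-hour grid, the chance of a false time over nine blood counts is 8% (2% missing, clustered) to 61% (10% missing, independent). Across the trial, at 5% missing, that is about 0.3 to 2.7 of 24 patients under the assumed shares, and fewer if status is derived daily. One such time can visibly shift the mean of a group of 6, but it threatens neither the primary safety objective nor any planned test. It is worth correcting before database lock because the correction is cheap.

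**What to change.** In SAP 7.6.1, define status at each time point as follows:
- Present: at least two observed components are met.
- Absent: met plus missing components total one or fewer.
- Not evaluable: anything else.

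A not-evaluable time point cannot count as resolution or as a SIRS-free time point, and resolution is the first time point classed absent. The respiratory component counts as observed when respiratory rate is recorded, and the white cell component when the count is recorded.

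The alternative is to apply the 7.3.1 rule (most recent earlier WBC) in 7.6.1, so that both SIRS outputs share one WBC rule. Whichever is chosen, reconcile 7.6.1 with 7.3.1. State also whether status is derived every 12 hours or daily, and how a SIRS-free day is counted.

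The cost is SAP wording and programming, with no new data. Under the not-evaluable rule some time points drop out, and a true resolution can be recorded one assessment late when exactly one observed criterion is met and WBC is missing. On a 12-hour grid with independent misses the expected delay is 12p/(1 − p) = 0.24, 0.63 or 1.33 h at 2%, 5% or 10% missing. It is longer from Day 6, when blood counts are daily. Unmeasured PaCO2 or band forms would still be treated as not met.
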